8.10 Changes to Protocol-Specified Analyses

The protocol stated that a subject would be deemed compliant if the subject has taken 80% to 100% of the expected tablets; however, this was changed, and a subject will be deemed to be compliant if the subject has taken 80% to 105% of the expected tablets.

TMC and the total motor score from the UHDRS were listed as safety parameters in the protocol; however, these parameters were changed to efficacy endpoints for this SAP.

9 Statistical Analyses

9.1 Subject Disposition

The number and percent of enrolled subjects who were screen failures, who were included in the Safety Population, who completed the study, and who withdrew from the study, and their primary reason for withdrawal, will be summarized. Subject disposition will be summarized using all enrolled subjects. Enrolled subjects are those subjects who signed the informed consent form.

For screen failures, the reason that subjects were declined and the reason that subjects were excluded from the study will be summarized using counts and percentages.

A listing summarizing whether subjects completed or discontinued from the study will also be presented, and the primary reason for discontinuation will be provided for those subjects who withdrew.

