6 STUDY METHODS AND PROCEDURES

6.1 Screening Period

6.1.1 Screening Visit (up to Week -4) (Switch Subjects)

See the Schedule of Events A for a detailed summary of activities.

Prior to conduct of any study-specific screening procedures, the Investigator, or designee, will explain to the subject and caregiver the study procedures, including the risks involved and the fact that their participation is voluntary. If the subject lacks the capacity to provide informed consent (as determined by an independent assessment by a qualified healthcare provider not directly involved in other study activities), a legally authorized representative must provide written informed consent and the subject must provide assent. Each subject and caregiver will acknowledge receipt of this information by signing and dating a current, IRB/IEC-approved written informed consent, or subject assent if an LAR is utilized, for their involvement in the study in the presence of the Investigator, or designee, who will also sign and date the informed consent or assent. A Research Advance Directive (See Section 6.12) will be obtained from

subjects with the ability to self consent. Subjects rolling over from the SD-809-C-15 study may have capacity assessment/informed consent/assent/research advance directive obtained up to 30 days in advance of subject's First-HD Week 13 Visit/ARC-HD Baseline Visit.

Each potentially eligible subject who has signed an informed consent or assent and is screened will be assigned a Subject Identification (ID) Number in consecutive order by the site from the site-specific Subject Identification list provided to the site by the Clinical Trials Coordination Center (CTCC); this four-digit number will identify subjects on all study forms and lab specimens. Should the subject proceed to enrollment, the Subject ID Number will continue to be used for the subject through the duration of the study. For subjects who have signed the informed consent form and subsequently do not meet eligibility criteria or withdraw consent, the source record should contain at least minimum information as documentation of screen failure (i.e., demographics, eligibility criteria reviewed, procedures performed, etc.).

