6.1.3 Baseline Visit (Day 0)

See the Schedule of Events A and B for a detailed summary of activities.

Subjects will return to the clinic on Day 0 to undergo baseline evaluation. Subjects who continue to meet selection criteria will be enrolled in the study.

Subjects switching from tetrabenazine (Switch subjects)

Subjects will be converted from their TBZ regimen to an SD-809 ER regimen that is predicted to provide comparable exposure to total (α + β)-dihydrotrabenazine (α - and β -HTBZ). Subjects will continue taking their TBZ regimen through midnight of Day 0 and then directly switch to their assigned SD-809 ER regimen the next morning.

The **Switch** Baseline clinic visit will consist of the following:

Note: The italicized procedures listed immediately below should be done before PK blood sampling to assure the subject still qualifies for study participation:

- *Adverse events and concomitant medication use*
- *Collect and review diary card*
- *Urine pregnancy test (women of child-bearing potential only)*
- *Hospital Anxiety and Depression Scale (HADS)*
- *Columbia Suicide Severity Rating Scale (C-SSRS): Since Last Visit version*
- *Unified Parkinson's Disease Rating Scale (UPDRS): dysarthria item*
- *Swallowing Disturbance Questionnaire (SDQ)*

- *Physical examination, vital signs (including orthostatic blood pressure and pulse) and weight*
- *Baseline results will be assessed by the Investigator or Sub-Investigator and subjects who meet eligibility criteria will be enrolled into the study.*
- Clinical laboratory tests: serum chemistry, hematology, and urinalysis
- PK blood sampling for tetrabenazine (See Section 6.8)
- Administer tetrabenazine post pre-dose sampling (Switch subjects scheduled for morning visits only)
- Montreal Cognitive Assessment (MoCA[®])
- Complete Unified Huntington's Disease Rating Scale (UHDRS):
 - Motor
 - Cognitive
 - Behavior
 - Functional assessment
 - Independence
 - TFC
 - Summary
- Barnes Akathisia Rating Scale (BARS)
- Epworth Sleepiness Scale (ESS)
- Subjects will be provided with one week of study medication.
- Week 1 clinic visit will be scheduled.

Subjects from the SD-809-C-15 Study (Rollover subjects)

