- ** Data (Week 13) from Study SD-809-C-15 will be utilized as part of Baseline assessment. Additional specific activities required at this visit are denoted by an “X”
- 1 Assessment transferred from Screening or Baseline evaluation in Study SD-809-C-15
 - 2 Perform orthostatic blood pressure and pulse after subject is in standing position for at least 3 minutes.
 - 3 Assessments to be completed at Investigator’s discretion
 - 4 Brief physical examination, which includes evaluation of the cardiovascular, respiratory, and abdominal systems.
 - 5 The C-SSRS Since Last Visit version is administered at all visits for Rollover subjects
 - 6 Study medication supply will be ordered (See Operations Manual for further details).
 - 7 Subjects who withdraw early from the study should have a single blood sample collected for PK at the Early Termination Visit if the last dose was within the prior 48 hours, if possible. Subjects who experience an SAE should have a single blood sample collected for metabolites of SD-809 within 48 hours of SAE, if possible.
 - 8 For subjects on allowed doses of citalopram or escitalopram:
 - Week 2: A 12-lead ECG is required at this visit.
 - Week 4: If the dose of study drug has been increased since the last ECG, a 12-lead ECG is required at this visit.
 - 9 After Week 28, perform clinic visits every 13 weeks until the End of Treatment Visit. Obtain safety labs and urine pregnancy test every 26 weeks after Week 28, and perform UHDRS-TFC every 52 weeks after Week 28.
 - 10 For subjects requiring an Unscheduled Clinic Visit for any reason, assessments denoted with X should be performed; all other assessments are as indicated at Investigator’s discretion (see Section 6.5 of the protocol).

5 Data Management

Complete details of data management will be described in a separate Data Management Plan.

6 Definition of Population

Safety Population: The Safety Population will include all subjects who were administered any study drug. Subjects who are assigned a subject number but withdrew prior to dosing will not be included in the Safety Population. If relevant, details of their participation and reason for withdrawal will be listed separately in the CSR.

Unless specified otherwise, all data will be summarized for the Safety Population. In addition, two subsets of the Safety Population are defined:

- Rollover Cohort: Successfully completed SD-809-C-15 (First-HD) prior to enrollment into SD-809-C-16 (ARC-HD)

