8.7 Comments on Statistical Analysis

The following general comments apply to all statistical analyses and data presentations:

- Unless otherwise specified, all data will be summarized separately for the Rollover Cohort and the Switch Cohort.
- Summaries will include frequencies and percentages for categorical data and the number of observations, mean, standard deviation, median, minimum, and maximum for continuous data.
- Duration variables will be calculated using the general formula: (end date – start date) + 1.
- Unless specified otherwise, for subjects in the Switch cohort, the baseline value is the last available value prior to the first administration of SD-809 on Day 1. For Rollover subjects from the First-HD study, for assessments that were scheduled to be performed at Week 13 of that study or the Baseline visit of the ARC-HD study, the baseline value is the last available off-treatment (at least 4 days after the last administration of study drug) value prior to administration of SD-809 on Day 1. For assessments that were not scheduled to be performed at Week 13 of the First-HD study or at the Baseline visit of the ARC-HD study, the baseline value is the last available value prior to administration of study drug on Day 1 of the First-HD study. For the Switch cohort, the baseline value used for calculating change from baseline for TMC and the total motor score will be the mean of the values from the Screening and Baseline visits.
- If the reported value of a clinical laboratory parameter cannot be used in a statistical summary table (e.g., a character string is reported for a parameter of the numeric type), a coded value must be appropriately determined and used in the statistical analyses. In general, a value or lower or upper limit of normal range such as '<10' or '<5' will be treated as '10' or '5', respectively, and a value such as '>100' will be treated as '100.' However, the actual values as reported in the database will be presented in data listings.
- Individual subject listings of all data represented on the eCRFs will be provided to facilitate the investigation of tabulated values and to allow for the clinical review of all data.
- Version 9.4 of SAS statistical software package will be used to provide all summaries, listings, and graphs described in this document.

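### SAP 9.1 takes completion and withdrawal percentages over everyone who signed consent, so never-dosed screen failures pull both below the rates in treated subjects

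*SAP*

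**What the plan says.** SAP 9.1 (Subject Disposition) puts the screening and treatment outcomes into one summary: "The number and percent of enrolled subjects who were screen failures, who were included in the Safety Population, who completed the study", followed by those who withdrew and the primary reason. It then fixes the base: "Subject disposition will be summarized using all enrolled subjects", and "Enrolled subjects are those subjects who signed the informed consent form".

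The protocol uses the word more narrowly. In Protocol 6.1.3 enrollment follows the Baseline eligibility check: "Subjects who continue to meet selection criteria will be enrolled in the study". Protocol 6.1.1 asks for screen-failure documentation in these cases: "For subjects who have signed the informed consent form and subsequently do not meet eligibility criteria or withdraw consent".

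The treated set is defined in SAP section 6: "The Safety Population will include all subjects who were administered any study drug". The same section adds "In addition, two subsets of the Safety Population are defined", namely the Rollover and Switch cohorts. SAP 8.7 makes presentation by cohort the default: "Unless otherwise specified, all data will be summarized separately for the Rollover Cohort and the Switch Cohort".

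**The concern.** Completion and withdrawal are outcomes of treatment, so their natural denominator is the subjects who were treated. A person who signs consent and fails screening can neither complete treatment nor withdraw from it, yet SAP 9.1 counts that person in the base.

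The defaults elsewhere in the SAP do not correct this. The Safety Population default in section 6 gives way where another set is specified, and 9.1 specifies one. The general denominator rule in 8.7 does not override a base that 9.1 names.

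The definition also fits poorly with the rest of the SAP. Section 9.6 treats enrolling an ineligible subject as a protocol deviation. Under the 9.1 definition, every consented subject who failed eligibility would be such a deviation.

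What is at stake is the only planned summary of overall completion, total withdrawal and withdrawal for reasons other than adverse events. In an open-ended safety study these rows tell the reader how long treatment was sustained and why it stopped. The AE-withdrawal row could also show a different percentage from the TEAE table for the same subjects.

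**Working it through.** The plan states no screen-failure or withdrawal rate, so it has no figure of its own to reproduce. The planned cohort sizes do add up: 36 + 80 = 116 (Protocol section 3).

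**Inputs**
- Dosed subjects: about 36 Switch and 80 Rollover (Protocol section 3).
- w = withdrawal rate among treated subjects; 20% and 30% are assumed for illustration.
- s = screen failures as a share of consent-signers; 10%, 20% and 30% are assumed.
- Everyone who consents but is not dosed is coded as a screen failure and not as a withdrawal, in line with Protocol 6.1.1.

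**Formula.** With N treated subjects there are N/(1 − s) consent-signers. The 9.1 withdrawal percentage is wN ÷ [N/(1 − s)] = w(1 − s). Completion is (1 − w)(1 − s). The two add to 1 − s instead of 100%.

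**Case A: s applies to the whole study**

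| s | Withdrawal, true 20% | Completion, true 80% | Sum | Withdrawal, true 30% |
|---|---|---|---|---|
| 10% | 18% | 72% | 90% | 27% |
| 20% | 16% | 64% | 80% | 24% |
| 30% | 14% | 56% | 70% | 21% |

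**Case B: failures in Switch only, pooled table, w = 20%.** Withdrawals number 0.20 × 116 = 23.2.

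| Switch s | Switch consent-signers | Total base | Pooled withdrawal shown |
|---|---|---|---|
| 10% | 36/0.9 = 40 | 120 | 23.2/120 = 19.3% |
| 20% | 36/0.8 = 45 | 125 | 23.2/125 = 18.6% |
| 30% | 36/0.7 = 51.4 | 131.4 | 23.2/131.4 = 17.7% |

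In Case B the pooled understatement is about 0.7 to 2.3 percentage points.

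**Case C: by cohort.** Assume 9/36 Switch and 20/80 Rollover withdrawals, 25.0% in each. If 9 Switch screen failures are placed in the Switch column and Rollover has none, the table shows 9/45 = 20.0% against 20/80 = 25.0%. If both cohorts have the same s, say 20%, a true 20% is shown as 16% in both and the difference stays zero.

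**Case D: sensitivity to coding.** Take the same 45 Switch consent-signers and 9 on-treatment withdrawals. If 3 of the 9 never-dosed subjects were coded as withdrawn, the row shows 12/45 = 26.7%, above the treated-subject rate of 9/36 = 25.0%. The understatement therefore rests on the coding assumption above.

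**With the Safety Population as base** the withdrawal percentage is w and completion is 1 − w in each cohort, whatever s is.

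**The case against.** The strongest reply is that the tolerability endpoint is unaffected. SAP 7.2 specifies AEs leading to withdrawal. SAP 9.9 and 9.9.1 summarize them on the Safety Population by study period, including treatment-related cases and a composite with dose reduction and suspension. Exposure-adjusted rates and a listing are added. This stands. A reader might infer that the plan makes the drug's tolerability look better than it is, but the documents do not support that. The pre-specified measure has a treated-subject base, and the 9.1 base lowers completion as well, which is unfavourable to the sponsor.

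The second reply is that nothing is lost, because the same table reports the Safety Population count and a reader can recompute. That is true and limits the harm. It does not justify printing percentages that describe neither the screened nor the treated group well.

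A reader might also infer that the Switch versus Rollover comparison is distorted, as in Case C. That is possible but not shown. It needs unequal screen-failure rates, and the documents give none. SAP 8.8 gives a Screening Period to Switch subjects only, which makes unequal rates plausible. However, Rollover consent may be taken up to 30 days before Baseline, so failures can occur there too. It also needs never-dosed subjects to be assigned to a cohort, while section 6 defines both cohorts within the Safety Population and does not say where such subjects belong. SAP 8.1 plans no formal comparison.

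Finally, the SAP states its meaning of enrolled in the same paragraph, and the protocol sets no disposition denominator. No protocol-specified analysis is contradicted, so the difference in terms is a matter of clarity.

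**Conclusion.** The point holds for the disposition table. As SAP 9.1 is written, completion, withdrawal and reason-for-withdrawal percentages equal the treated-subject rates multiplied by (1 − s). The actual size is unknown because s is not given. For a true 20% withdrawal rate, the assumed ranges give 18–14% if 10–30% of all consent-signers fail screening, and about 19.3–17.7% if failures occur only in Switch. Both ranges assume that never-dosed subjects are coded as screen failures.

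The rows affected are overall completion, total withdrawal and non-AE reasons, together with an AE-withdrawal percentage that could differ from the TEAE table. This is a defect of reporting with modest weight. It biases no safety endpoint, and a cohort distortion remains unproven.

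**What to change.** Amend SAP 9.1 as follows:
- Use consented subjects as the base for the screen-failure and Safety Population rows only.
- Report completion, withdrawal and primary reason for withdrawal as a percentage of the Safety Population, for Rollover, Switch and overall.
- Call the wider set consented or screened, and keep enrolled for the protocol's meaning, so that the deviation category in 9.6 also reads correctly.

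This needs no new data, a few sentences in the SAP and a trivial programming change. If there are screen failures, withdrawal percentages become slightly higher and completion percentages rise too. The two can then be read against 100% of treated subjects, and the AE-withdrawal row shares its base with the TEAE summary for the entire treatment period.

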9.2 Demographic and Baseline Characteristics

Descriptive statistics or counts and percentages, as appropriate, will be used to summarize demographic and baseline characteristics in the Safety Population. Subject demographics include age, gender, race, ethnicity, education (years), CAG repeat length, height, weight, and body mass index (BMI) at screening, whether or not the subject was a CYP2D6 poor metabolizer, and disease duration (in years). Age (in years) will be calculated from the date of birth to the date of informed consent in Protocol SD-809-C-16 for both Switch and Rollover subjects. Age will be reported as an integer. BMI will be calculated using the following formula: $BMI (kg/m^2) = weight (kg)/(height (m))^2$. Only the year of diagnosis is collected in the CRF, so disease duration (years) will be calculated using the following formula: (Date of Informed Consent - July 1 of Year of Diagnosis)/365.25.

All demographic and baseline characteristics will also be listed.

9.3 Medical History

Medical history will be obtained at Screening for C-16 Switch subjects and recorded in the eCRF and transferred from data collected in C-15 for Rollover subjects.

Medical history information will be summarized by Medical Dictionary for Regulatory Activities (MedDRA) high level group term and preferred term using counts and percentages. Medical history information will also be listed.

9.4 Concomitant Medications

Concomitant medications are defined as medications taken any time after the start of dosing until the final visit. Medications are also considered concomitant if their stop date is unknown or marked as continuing. Medications with missing start dates will be considered ongoing on the first day of study drug administration, except where positive confirmation is available that the medication was stopped before study drug administration.

The World Health Organization Drug Dictionary (WHODRUG) will be used to classify prior and concomitant medications by therapeutic class and preferred term. The WHODRUG version will be noted in the CSR. The number and percentage of subjects receiving concomitant medications will be summarized by Anatomical Therapeutic Chemical (ATC) level 3 and preferred term. Subjects will be counted only once for an ATC class, even if the subject took the same medication on multiple occasions or more than one medication in the same ATC class. Similarly, subjects will be counted at most once for a preferred term, even if they took the same medication on multiple occasions or more than one medication with the same preferred term. The number and percentage of subjects receiving concomitant medications at baseline will also be summarized by ATC level 3 and preferred term.

A listing of concomitant medications will also be presented.

9.5 Study Drug Exposure and Compliance

The Investigator or designated study staff is responsible for monitoring the subject's compliance with study drug during the trial. Compliance will be assessed by tablet count obtained from returned study drug containers and must be reviewed at every visit while the subject is still in the clinic to determine if the subject is taking study drug as directed.

Percent compliance in the interval between visits will be calculated as $100 \cdot (\text{number of tablets used} / \text{number of tablets expected to be used})$, where $\text{number of tablets used} = \text{number of tablets dispensed} - \text{number of tablets returned}$. A subject will be deemed compliant if the subject has taken 80% to 105% of the expected number of tablets of study drug; this definition of compliance supersedes the definition specified in the study protocol.

For Switch subjects, percent compliance will be summarized for the following time periods using descriptive statistics: from Day 1 to the Week 4 visit, from Day 1 to the Week 8 visit, and from Day 1 to the last dose of study drug. For Rollover subjects, percent compliance will be summarized for the following time periods using descriptive statistics: from the Day 1 to the Week 8 visit and from Day 1 to the last dose of study drug. Compliance will be summarized for these same time periods using counts and percentages.

The length of time (in days) that each subject is exposed to SD-809 will be summarized using descriptive statistics. For subjects who complete the study through Week 8, the duration of time in days from Day 1 until the day of first receiving the SD-809 dose received at Week 8 (i.e., the duration of time to achieve a stable dose of SD-809) will be summarized using descriptive

statistics. For Switch subjects who complete the study through Week 8, the number and percentage of subjects who achieve a stable dose by Week 4 (i.e., received the same dose of SD-809 at Week 4 that they received at Week 8) will be presented.

For each subject, the initial dose, titrations, and investigator-initiated dose changes that occur during the study will be listed.

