This Statistical Analysis Plan (SAP) describes the planned statistical analyses to be performed for the analysis of data from Protocol SD-809-C-16, “An Open-Label, Long Term Safety Study of SD-809 ER in Subjects with Chorea Associated with Huntington Disease.” All of the analyses specified in this SAP will be included in the final Clinical Study Report (CSR).

The structure and content of this SAP provides sufficient detail to meet the requirements identified by the FDA and International Conference on Harmonization of Technical Requirements for Registration of Pharmaceuticals for Human Use (ICH): Guidance on Statistical Principles in Clinical Trials. The following documents were reviewed in preparation of this SAP:

- Final Clinical Protocol SD-809-C-16, Amendment 03, issued 02 March 2015
- Case report forms (CRFs) for Protocol SD-809-C-16, issued 18 January, 2017

Throughout this SAP, SD-809 extended release will be denoted simply as SD-809.

2 Purpose of the Analyses

The purpose of this SAP is to outline the planned analyses to be completed to support the final Clinical Study Report (CSR) for Protocol SD-809-C-16. The planned analyses identified in this SAP will be included in regulatory submissions and/or future manuscripts. Also, exploratory analyses not necessarily identified in this SAP may be performed to support the clinical development program. Any post-hoc or unplanned analyses not identified in this SAP will be clearly identified in the CSR.

3 Study Objectives

The objectives of this study are as follows:

- Evaluate the safety and tolerability of titration and maintenance therapy with SD-809
- Evaluate the safety and tolerability of switching subjects from tetrabenazine to SD-809
- Evaluate the pharmacokinetics of tetrabenazine, SD-809 and their respective α - and β -metabolites in subjects switching from tetrabenazine to SD-809

4 Study Design

This is an open-label, single-arm study in which subjects with manifest Huntington’s disease (HD) who are receiving FDA-approved doses of tetrabenazine (TBZ) for the treatment of chorea associated with HD or have successfully completed the SD-809-C-15 efficacy study will be invited to participate. Successful completion of Study SD-809-C-15 is defined as (1) study participation through Week 13, (2) the subject has generally been compliant with study drug and

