7.2 Safety Endpoints

Safety and tolerability will be assessed throughout the study by monitoring the following:

- Incidence of adverse events (AEs), serious AEs (SAEs), severe AEs, drug-related AEs, and AEs leading to withdrawal during the following periods:
 - The entire post-baseline period
 - During the Titration Period (from Day 1 to the end of Week 8) in Rollover subjects
 - During the Dose-Adjustment Period (from Day 1 to the end of Week 4) in Switch subjects
 - During the Extended Dose-Adjustment Period (from Day 1 to the end of Week 8) in Switch subjects who undergo dose adjustment between Weeks 4 and 8 (if at least 10% of Switch subjects have had a dose adjustment between Week 4 and Week 8)
 - During the Stable-Dose Period (Week 8 to end of study)
- Observed values and changes from baseline in clinical laboratory parameters (hematology, chemistry, and urinalysis)
- Observed values and changes from baseline in vital signs
- Observed values in ECG parameters and abnormal findings

- Numbers of subjects with QTcF values > 450 msec, > 480 msec, > 500 msec
- Counts and percentages for Columbia Suicide Severity Rating Scale (C-SSRS)
- Observed values and changes from baseline in the following:
 - Unified Huntington Disease Rating Scale (UHDRS)
 - Unified Parkinson's Disease Rating Scale (UPDRS) (dysarthria)
 - Barnes Akathisia Rating Scale (BARS)
 - Hospital Anxiety and Depression Scale (HADS)
 - Epworth Sleepiness Scale (ESS)
 - Montreal Cognitive Assessment (MoCA[®])
 - Swallowing Disturbance Questionnaire (SDQ)
- Duration of time to achieve a stable dose of SD-809, defined as the number of days from Day 1 until the first day at which the subject was taking the dose level they were receiving at Week 8.

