8.5.2 Missing Endpoint Data

Missing endpoint data will not be imputed, and only observed data will be summarized.

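### Both stable-dose summaries in SAP 9.5 cover only subjects who complete Week 8, so Switch subjects who stop during dose adjustment leave the denominator, and SAP 8.10 does not declare the change

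*SAP*

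**What the plan says.** SAP 9.5 (Study Drug Exposure and Compliance) sets out two stable-dose summaries. Both are limited to Week 8 completers.

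- Time to stable dose, both cohorts: "For subjects who complete the study through Week 8, the duration of time in days from Day 1 until the day of first receiving" the Week 8 dose.
- Percentage stable by Week 4, Switch cohort: "For Switch subjects who complete the study through Week 8, the number and percentage of subjects who achieve a stable dose by Week 4". Stable by Week 4 means the subject "received the same dose of SD-809 at Week 4 that they received at Week 8".

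SAP 7.2 lists time to stable dose as a safety endpoint and anchors it to "the first day at which the subject was taking the dose level they were receiving at Week 8". A subject who stops before Week 8 has no such dose and so no value. SAP 8.5.2 adds: "Missing endpoint data will not be imputed, and only observed data will be summarized".

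The general rules point to a wider set. SAP 6 says: "Unless specified otherwise, all data will be summarized for the Safety Population". Protocol 8.1 places all safety-endpoint summaries in the Safety Population, meaning everyone given any study drug. Protocol 8.4 includes time to stable dosing among those endpoints. SAP 9.9.7 keeps it among the safety outcomes, and SAP 9.9 says safety is assessed in the Safety Population. SAP 8.10 lists two changes from the protocol's analyses: the compliance limits, and the move of the chorea and motor scores to efficacy. The Week 8 restriction is not there.

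**The concern.** One objective (SAP 3) is to "Evaluate the safety and tolerability of switching subjects from tetrabenazine to SD-809". Protocol 3.2 expects Switch subjects to reach their target dose faster than Rollover subjects and allows up to 4 weeks of adjustment. The Week 4 percentage describes how that worked out.

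Some failures are foreseeable. Protocol 5.2.2 says that subjects with diminished CYP2D6 function may start up to 30-40% below their tetrabenazine exposure. Protocol 6.13 allows withdrawal for intolerable adverse events. SAP 8.8 anticipates withdrawal during the Extended Dose-Adjustment Period. A Switch subject who stops at Week 2, 5 or 7 because the conversion did not work is informative about the switch, yet appears in neither the numerator nor the denominator. A reader who takes the percentage as describing everyone who was switched would be reading a figure for those who stayed.

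**Working it through.** The documents state no figure to reproduce, so this is direct arithmetic with the assumptions marked.

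**Inputs**
- N, Switch subjects dosed: 36. Protocol 3 plans approximately 36; the exact number is an assumption.
- w, Switch subjects who stop before Week 8: not given. Assumed 0, 1, 2 and 4.
- S, completers on the same dose at Weeks 4 and 8: not given. Assumed 26.

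**Formulas**
- Plan's percentage: S/(N-w).
- All-dosed percentage if every early stopper counts as not achieved: S/N.
- All-dosed percentage if every early stopper counts as achieved: (S+w)/N.
- Ratio of the plan's percentage to S/N: N/(N-w), which is at least 1.

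**Results for N = 36, S = 26**

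| w | Plan: S/(N-w) | Low: S/N | Plan minus low | High: (S+w)/N | N/(N-w) |
|---|---|---|---|---|---|
| 0 | 26/36 = 72.2% | 72.2% | 0 | 26/36 = 72.2% | 1.00 |
| 1 | 26/35 = 74.3% | 72.2% | 2.1 points | 27/36 = 75.0% | 1.03 |
| 2 | 26/34 = 76.5% | 72.2% | 4.2 points | 28/36 = 77.8% | 1.06 |
| 4 | 26/32 = 81.3% | 72.2% | 9.0 points | 30/36 = 83.3% | 1.13 |

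Holding S at 26 makes the completer percentage climb as w rises. If the completer percentage is instead held at 75%, w = 4 gives 24/32 = 75.0% against 24/36 = 66.7%, a difference of 8.3 points. The factor N/(N-w) is the same either way.

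The plan's figure always lies between the low and high values. It is at least S/N because N-w is no larger than N. It is at most (S+w)/N because adding w to both the numerator and the denominator of a proportion cannot lower it.

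**Time to stable dose.** Early stoppers have no defined value and no handling rule is given. The summary is therefore conditional on completing Week 8. Nothing in the documents allows the direction or size of an effect on the mean or median to be computed.

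**The case against.** The case for leaving the plan alone has real content.

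- **The percentage is not the designated measure of the switch objective.** A reader might infer that it is. The documents do not say so: it sits in the exposure section, is absent from the endpoint list in SAP 7.2 and is never called a success rate. Adverse events by dose-adjustment period also address that objective, and SAP 8.6 gave the adequacy of the conversion strategy to an interim analysis whose details are not visible in Appendix 1. This stands.
- **The direction is not fixed.** A reader might infer that the restriction can only inflate the result. That holds only if early stoppers count as not achieved. A subject could hold one dose from Day 1 and leave for an unrelated reason; Protocol 6.13 includes voluntary withdrawal, loss to follow-up and pregnancy. The completer figure lies inside the all-dosed bounds. This stands.
- **The restriction is disclosed, and withdrawals are reported elsewhere.** SAP 6 permits exceptions. The count accompanies the percentage, so S/N can be recovered from the cohort size. Disposition gives reasons for withdrawal (SAP 9.1), adverse events leading to withdrawal are summarised by period (SAP 9.9.1), and dose changes are listed by subject. This softens the point but does not remove it. Disposition is not planned by period, and adverse-event tables miss a withdrawal for lost chorea control that was not recorded as an adverse event. Neither is joined to the stable-dose result.
- **The definition needs a Week 8 dose.** That explains why an early stopper has no dose match. It does not prevent showing that subject in a separate withdrawn row.

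**Conclusion.** The denominator point holds. For time to stable dose, the Week 8 restriction departs from Protocol 8.1 and SAP 8.10 does not declare it. For the Week 4 percentage, which is not itself a listed endpoint, it is an unexplained exception to the Safety Population default in SAP 6. In both cases, subjects who stop during dose adjustment are left out.

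The size is conditional. With early stoppers counted as not achieved, N = 36 and S = 26, the gap runs from 0 points (w = 0) to 9.0 points (w = 4). N is the planned approximate number; S and every value of w are assumptions. Without a rule for early stoppers, the all-dosed value is known only to lie between S/N and (S+w)/N.

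Two stronger conclusions are not supported. One is that time to stable dose is biased in a favourable direction: the documents show only that it is conditional on Week 8 completion. The other is that the restriction spoils a comparison between cohorts: no formal analysis is planned (SAP 8.1), cohorts are summarised separately (SAP 8.7), and they differ by design in starting dose and titration length. The analysis is descriptive, so what is at stake is how the switch results are read, not a test.

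**What to change.** In SAP 9.5, use all dosed Switch subjects as the denominator for the Week 4 percentage and show three rows that sum to it:

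1. stable by Week 4;
2. not stable by Week 4;
3. withdrawn before Week 8, by reason, not counted as achieved.

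Keep the completer percentage as a secondary figure. Label time to stable dose as conditional on Week 8 completion, and show beside it, for each cohort, how many subjects were excluded and why. List the restriction in SAP 8.10.

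A cumulative-incidence analysis with withdrawal as a competing event is not part of this request. Stability is defined backwards from the Week 8 dose, so that analysis would need a new event definition.

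The cost is a short text edit, one more table row with the accompanying exclusion counts, and a headline percentage that is slightly less favourable if anyone stops early. Disposition data and the dose listings already planned supply what is needed.
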